### 6.2.1.3. Vital sign measurements

Absolute values and changes from baseline in supine systolic and diastolic BP, and PR will be summarized by treatment group and timepoint, according to sponsor reporting standards. Tables will be paged by parameter.

Maximum decrease from baseline for supine systolic and diastolic blood pressures and maximum increase from baseline for supine pulse rate will be summarized by treatment group, according to sponsor reporting standards.

Maximum absolute values and changes from baseline for vital signs will also be summarized descriptively by treatment group using categories as defined in [Appendix 1](#). Numbers and percentages of participants meeting the categorical criteria will be provided. All planned and unplanned post dose time points will be counted in these categorical summaries. All values meeting the criteria of potential clinical concern will be listed.

### 6.2.1.4. Clinical safety laboratory measurements.

Laboratory data will be listed and summarized by treatment group and overall, in accordance with the sponsor reporting standards.

### **6.2.2. Baseline adjusted QTcF of moxifloxacin and placebo at Tmax of 3, 4, and 5 hours on Day 3.**

Change from baseline in QTcF will be analyzed by MMRM as described in Section 5.2.4 using ECG analysis set. All planned post-dose time points on Day 3 and 4 of each period will be included in the model. The least-squares (LS) means of change from baseline QTcF of moxifloxacin and placebo, as well as the difference between moxifloxacin and placebo, and the corresponding 90% CIs will be reported for each post-dose timepoint. The 96.7% CIs for mean differences between moxifloxacin and placebo at 3, 4, and 5-hr pose-dose will also be provided as the Bonferroni-adjusted two-sided 90% CIs.

A visualization displaying the model predicted mean difference in change from baseline QTcF between moxifloxacin and placebo and the corresponding 90% CIs will also be created.

*The study will be deemed adequately sensitive to detect QT/QTc prolongation if any of the lower limits of the two-sided Bonferroni-adjusted 90% CI (96.7% CI) for mean differences between moxifloxacin and placebo at any of the 3, 4 and 5-hr pose-dose, respectively, are greater than 5 msec.*

### **6.3. Other Endpoint(s)**

#### **6.3.1. Baseline adjusted heart rate, PR interval, and QRS intervals of sisunatovir and placebo at each postdose time point.**

Absolute values and changes from baseline for the HR, PR interval, QT interval, and QRS intervals will be summarized by treatment group and timepoint as described in Section 6.2.1.2.

The difference of ECG parameters, including uncorrected QT, QTcF, QTcB, HR, PR, and QRS, between active drugs (sisunatovir and moxifloxacin) and placebo for each participant will be summarized by post-dose timepoints. The time matched mean difference and the corresponding 90% CIs will be reported for each post-dose dose timepoint. Plots of time matched mean difference between active drugs and placebo (Y-axis) against time post-dose (X-axis) will also be provided.

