3. OBJECTIVES AND ENDPOINTS

Objectives	Endpoints
Primary:	Primary:

To evaluate the effect on QT interval corrected for heart rate (QTc) interval in healthy participants, of possible clinical therapeutic concentrations of sisunatovir compared with placebo.	
Placebo-corrected, baseline adjusted QTc interval using Fridericia's correction method (QTcF) of sisunatovir at expected maximum concentrations (C_{max}) at the CCI [REDACTED].
Secondary:	Secondary:

To evaluate the safety and tolerability at possible clinical therapeutic concentrations of sisunatovir, including but not limited to cardiovascular safety.To determine study sensitivity by comparing the effect of moxifloxacin 400 mg on QTc interval with placebo at historical moxifloxacin time for maximum observed concentration (T_{max}) of 3-5 hours.	
Adverse event (AE), ECG assessments, vital sign measurements, and clinical safety laboratory measurements.Baseline adjusted QTcF of moxifloxacin and placebo at T_{max} of 3, 4, and 5 hours on Day 3.
Exploratory:	Exploratory:

To evaluate the effect of sisunatovir on the electrocardiogram (ECG) parameters of, heart rate, PR interval and QRS interval.To evaluate the plasma pharmacokinetics (PK) of sisunatovir following multiple oral doses.To explore PK of sisunatovir by microsampling technique.	
Baseline adjusted heart rate, PR interval, and QRS intervals of sisunatovir and placebo at each postdose time point.Plasma sisunatovir parameters, including C_{max}, T_{max} and area under the plasma concentration-time profile from time 0 to 24 hours (AUC₂₄) post-dose on Day 3.Concentration of sisunatovir from paired samples obtained via microsampling compared to venous sampling.

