9.3.1.2. ECG Data Summaries

Mean baseline and changes from baseline for QTcF, QTcB, QT (uncorrected), PR, QRS and heart rate will be calculated for each participant and summarized descriptively (N, mean, standard deviation [SD], median, minimum and maximum) by treatment and time postdose.

Placebo-corrected change from baseline for QTcF, QT (uncorrected) and heart rate differences will be summarized (N, mean, 90% CI) and plotted (mean) for each treatment and time point postdose.

Categorization of HR, QRS, and PR intervals will be described in the SAP. Categorization of maximum QTc will be provided for QTcF by treatment using the following criterion.

Absolute Maximum (msec)	<450	450 to <480	480 to <500	≥500
Maximum Increase from Baseline (msec)	<30	30 to <60	>60	

If any of the 3 individual ECG tracings has a QTcF value ≥500 msec, but the mean of the triplicates is < 500 msec, the data from the participant's individual tracing will be described in a safety section of the study report in order to place the ≥500 msec value in appropriate clinical context. However, values from individual tracings within triplicate measurements

PFIZER CONFIDENTIAL

CT02-GSOP Clinical Pharmacology Protocol Template (01 April 2022)

Page 68

that are ≥ 500 msec will not be included in the categorical analyses unless the average from the triplicate measurements is also ≥ 500 msec.

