### 3.3. Other Endpoint(s)

#### 3.3.1. Baseline adjusted heart rate, PR interval, and QRS intervals of sisunatovir and placebo at each postdose time point.

Changes from baseline in heart rate, PR interval, and QRS interval of each participants in the treatment periods of sisunatovir and placebo at each postdose time point will be calculated. See [Section 3.1.1](#) for baseline and calculation details.

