### 3.4. Baseline Variables

- Baseline QTcF covariate for c-QT analysis

Baseline will be defined as the mean of the 3 average triplicate measurements taken at approximately 40 min, 25 min, and 10 min before the pre-dose meal on Day 1 within each period. Denote the baseline QTcF of participant  $i$  in treatment  $j$  at time 0 as  $\overline{QTcF}_{ij0}$ . The centered baseline,  $QTc_{ij0} - \overline{QTc}_0$  will be used in the c-QT analysis, where  $\overline{QTc}_0$  is the *overall mean of  $QTcF_{ij0}$ , i.e., the mean of all the baseline (= time 0) QTcF values* from all participants. More details will be documented in a separate report and included as an Appendix to the CSR.

- Baseline ECG covariate for MMRM analysis

The pre-dose baselines (one for each treatment period) will be included as covariate in the MMRM analysis of ECG parameters.

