#### **5.2.4. Mixed Models Repeated Measures (MMRM) Analysis**

*Change from baseline in QTcF intervals will be analyzed using a MMRM model with sequence, period, treatment, time (post-dose timepoint) and treatment by time interaction as fixed effects, participants as a random effect, and baseline QTcF as the covariate. A compound symmetry covariance matrix will be fitted to the repeated times within participant (other covariance matrices will be considered if necessary), and the Kenward-Roger approximation will be used for estimating degrees of freedom. The ECG analysis set will be used for the MMRM analysis.*

Standard SAS output will be provided to support the statistical summary table for the analysis model, but will not be included in the CSR.

Example SAS code is provided in [Appendix 2](#).

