##### 6.1.1.2. Sensitivity/Supplementary Analyses

By time analysis (intersection-union test) will be provided as the supplementary analyses. Briefly, change from baseline in QTcF will be analyzed by MMRM as described in Section 5.2.4 using ECG analysis set. All planned post-dose time points on Day 3 and 4 of each period will be included in the model. The least-squares (LS) means of change from baseline QTcF of sisunatovir and placebo, as well as the  $\Delta\Delta\text{QTcF}$ , 5.2.1 and the corresponding 90% CIs will be reported for each post-dose timepoint. The LS means and 90% CI of  $\Delta\Delta\text{QTcF}$  (Y-axis) will be plotted against time post dose (X-axis).

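### SAP 6.3.1 contrasts HR, PR, QRS and QT with placebo by unmodelled paired differences, does not say these are of change from baseline, and gives QTcF a second set of 90% CIs

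*SAP*

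**What the plan says.** Protocol section 3 defines the exploratory ECG endpoint as "Baseline adjusted heart rate, PR interval, and QRS intervals of sisunatovir and placebo at each postdose time point". SAP 3.3.1 derives it as change from baseline: "Changes from baseline in heart rate, PR interval, and QRS interval of each participants in the treatment periods of sisunatovir and placebo".

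SAP 6.3.1 first summarises absolute values and changes from baseline by treatment and time. For the comparison with placebo it turns to "The difference of ECG parameters, including uncorrected QT, QTcF, QTcB, HR, PR, and QRS, between active drugs (sisunatovir and moxifloxacin) and placebo", taken for each participant, and adds: "The time matched mean difference and the corresponding 90% CIs will be reported for each post-dose dose timepoint". That sentence mentions neither change from baseline nor a model.

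Other places bear on the same contrast:

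- Protocol 9.3.1.2: "Placebo-corrected change from baseline for QTcF, QT (uncorrected) and heart rate differences will be summarized (N, mean, 90% CI". PR and QRS are not in that list.
- SAP 3.4: "The pre-dose baselines (one for each treatment period) will be included as covariate in the MMRM analysis of ECG parameters". It does not name the parameters.
- SAP 5.2.4 specifies the MMRM for QTcF only, with sequence, period, treatment, time and treatment-by-time as fixed effects, participant as random effect and baseline as covariate.
- SAP 6.1.1.2, for the sisunatovir contrast: "change from baseline in QTcF will be analyzed by MMRM as described in Section 5.2.4 using ECG analysis set", with 90% CIs at each time. SAP 6.2.2 does the same for moxifloxacin.
- The Appendix 2 code has a repeated statement with period-by-participant as subject and no random statement for participant.

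**The concern.** Three things do not fit together.

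- The sentence that carries the confidence intervals leaves open which quantity is differenced, although the endpoint is baseline adjusted. For PR and QRS no analysis sentence in either document closes the gap.
- SAP 3.4 assigns a baseline covariate to an analysis that, for parameters other than QTcF, is specified nowhere. The paired method leaves unused the period-specific baselines (nine pre-dose ECGs per period), has no period term, and needs both periods from each participant.
- QTcF is in the 6.3.1 list as well. The report will hold two by-time 90% CIs for the same contrasts, from methods that can give different answers, and nothing says which one governs.

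At stake are the precision and clarity of the HR, PR and QRS results. They have some interest here: Protocol 2.2.1 reports inhibition of Cav1.2 and Nav1.5, and Protocol 2.2.3 reports lower HR with longer PR and QRS in guinea pigs at the highest dose.

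**Working it through.** **The plan's own figure.** Section 6.3.1 states no number. The only SD in the documents is in Protocol 9.5: an intra-subject SD of 5.61 msec for change from baseline in QTcF, with 42 participants, a one-sided 5% paired t-test, and an expected effect of 10 msec against a threshold of 5.

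- SD of a paired difference = 5.61 × √2 = 7.93. SE = 7.93/√42 = 1.224. Noncentrality = (10 − 5)/1.224 = 4.08.
- Power from the noncentral t on 41 df = 99.1% (99.0% with 41 participants). The stated 99% is reproduced, so 5.61 is a per-period SD of change.
- 90% half-width of a paired change-score difference = 1.683 × 1.224 = 2.06 msec. This is for QTcF. No SD is given for HR, PR or QRS.

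**Gain from baseline adjustment.** Set the within-day variance of a triplicate mean to 1 and the day-to-day variance to k². The baseline averages three triplicates, so its within-day variance is 1/3. k is not in the documents; 0.5 to 1.5 is an assumed range. Variances of the active-minus-placebo difference:

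- absolute values: 2(k² + 1)
- change scores: 2(1 + 1/3) = 2.67
- baseline as covariate: 2[k² + 1 − k⁴/(k² + 1/3)]

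| k | absolute | change | adjusted | SE ratio, adjusted/absolute | SE ratio, adjusted/change |
|---|---|---|---|---|---|
| 0.5 | 2.50 | 2.67 | 2.29 | 0.956 | 0.926 |
| 1 | 4.00 | 2.67 | 2.50 | 0.791 | 0.968 |
| 1.5 | 6.50 | 2.67 | 2.58 | 0.630 | 0.984 |

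The interval narrows by 4, 21 or 37% against absolute values and by 7, 3 or 2% against change scores. On the QTcF scale, 2.06 msec would become 2.06 × 0.926 = 1.91, 1.99 or 2.03 msec. The 7% is a best case: it takes the baseline slope from within-participant variation alone. A random-effect fit also draws on variation between participants, so the gain at k = 0.5 can be smaller.

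**Period drift.** With six balanced sequences, two treatments are one period apart in four sequences and two apart in two. The mean squared separation is (4×1 + 2×4)/6 = 2. A linear drift of δ per period in the change from baseline averages out of the mean difference, but adds 2δ² to the variance that the paired interval uses. At k = 1:

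- δ = 0.5: √(2.50/3.17) = 0.889, or 11% narrower with a period term.
- δ = 1: √(2.50/4.67) = 0.732, or 27% narrower.

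Drift that moves baseline and post-dose values alike cancels in change scores and gives no such gain.

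**Does the Appendix 2 code deliver this?** Simulation: 42 participants, six sequences, one time point, 400 replicates, post-dose SD 5.61, and assumed baseline SD 4 and between-participant SD 15. In the third model participant enters as indicators. Mean 90% half-widths (msec):

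| SD of participants' true change | baseline/post-dose correlation | paired absolute | paired change | baseline, period and participant | Appendix 2 style, no participant |
|---|---|---|---|---|---|
| 0 | 0.2 | 2.06 | 2.28 | 2.01 | 2.23 |
| 0 | 0.5 | 2.05 | 1.82 | 1.77 | 1.79 |
| 4 | 0.2 | 2.04 | 2.27 | 2.00 | 2.61 |
| 4 | 0.5 | 2.03 | 1.84 | 1.78 | 2.28 |
| 8 | 0.2 | 2.04 | 2.25 | 1.98 | 3.54 |
| 8 | 0.5 | 2.05 | 1.82 | 1.76 | 3.27 |

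With the participant effect, the model is narrowest in every row. Without it, the interval is wider than the paired ones once participants differ in true change.

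**The case against.** The strongest reply is that 6.3.1, read in context, already means change from baseline. Its heading says baseline adjusted, SAP 3.3.1 defines the variable that way, Protocol 9.3.1.2 describes a placebo-corrected change from baseline for QTcF, QT and HR, and SAP 2.1 declares no departure from the protocol. On that reading the gain without drift is 2 to 7%, under assumed variances. I accept this as the more natural reading. A reader might infer that absolute values are compared and the endpoint is not analysed as defined. The documents do not support that, since the first sentence of 6.3.1 summarises the endpoint itself. The ambiguity remains, most clearly for PR and QRS.

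A reader might also infer that SAP 3.4 promises an MMRM for HR, PR and QRS. It names no parameter, and limiting it to QTcF would remove the mismatch equally well.

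Nor do the two QTcF sets threaten a conclusion. The primary decision uses the concentration-QTc model, and assay sensitivity uses the 96.7% limits from the MMRM. The protocol itself foresaw a descriptive placebo-corrected QTcF summary. The check for no HR effect in SAP 5.2.3 is a plot and does not depend on the width of a 6.3.1 interval.

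Finally, balance protects the mean difference from period effects, and 2% dropout costs about one participant. Both are true. Balance does not, however, take drift out of the paired standard error.

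**Conclusion.** The point holds as a low-severity improvement. The placebo contrasts in 6.3.1 are unmodelled paired differences, the differenced quantity is not stated, SAP 3.4 and 5.2.4 disagree on the scope of the MMRM, and QTcF has duplicate by-time intervals that may differ, without stated precedence.

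The gain in precision is about 2 to 7% against paired change scores and 4 to 37% against absolute values, for an assumed day-to-day to within-day SD ratio of 0.5 to 1.5. It is larger only if change from baseline drifts across periods: 11 to 27% for an assumed linear drift of 0.5 to 1 within-day SD per period at a ratio of 1. All of this requires a participant effect in the model. The widths for HR, PR and QRS themselves cannot be computed from the documents.

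Two stronger conclusions do not follow: that the stated intervals are materially too wide, or that the two QTcF sets could change the study's conclusion.

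**What to change.** - In SAP 6.3.1, state that the contrasts with placebo are of change from baseline.
- For HR, PR, QRS and uncorrected QT, estimate them with the 5.2.4 model: sequence, period, treatment, time, treatment-by-time, the parameter's own period baseline, and participant as random effect. Report LS-mean differences with 90% CIs by time, and name these parameters in SAP 3.4.
- Before reuse, add to the Appendix 2 code the participant random effect that 5.2.4 already states.
- Label the paired QTcF summary descriptive, and state that 6.1.1.2 and 6.2.2 give the governing QTcF limits.

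If the sponsor prefers to keep the paired method, the minimum is to state change from baseline in 6.3.1, limit SAP 3.4 to QTcF, and label the QTcF summary as above.

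The cost is SAP wording, a small program correction and a few more model runs. No new data are needed, because the baselines are already collected.

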#### **6.3.2. Plasma sisunatovir parameters, including $C_{max}$ , $T_{max}$ and area under the plasma concentration-time profile from time 0 to 24 hours ( $AUC_{24}$ ) post-dose on Day 3.**

The PK parameter listed in the Table 3 will be summarized descriptively by treatment.

**Table 3. PK Parameters**

Parameter	Summary Statistics
$C_{max}$	N, arithmetic mean, median, cv%, standard deviation, minimum, maximum, geometric mean and geometric cv%.
$T_{max}$	N, median, minimum, maximum.

AUC 24	N, arithmetic mean, median, cv%, standard deviation, minimum, maximum, geometric mean and geometric cv%.
AUC 12 *	N, arithmetic mean, median, cv%, standard deviation, minimum, maximum, geometric mean and geometric cv%.

\*To be comparable with Microsampling.

Box and whisker plots for individual subject parameters (AUC24 and Cmax) will be presented and overlaid with geometric means.

Presentations for sisunatovir concentrations will include:

- a listing of all concentrations sorted by subject ID and nominal time postdose. The concentration listing will also include the actual times. Deviations from the nominal time will be given in a separate listing.
- a summary of concentrations by nominal time postdose, where the set of statistics will include n, mean, median, standard deviation, coefficient of variation (cv), minimum, maximum and the number of concentrations above the lower limit of quantification.
- median concentrations time plots (on both linear and semi-log scales) against nominal time postdose (based on the summary of concentrations by time postdose).
- mean concentrations time plots (on both linear and semi-log scales) against nominal time postdose (based on the summary of concentrations by time postdose).
- individual concentration time plots by treatment (on both linear and semi-log scales) against actual time postdose.
- individual concentration time plots by subject (on both linear and semi-log scales) against actual time postdose (there will be separate plots for each subject per scale).

For summary statistics, median and mean plots by sampling time, the nominal PK sampling time will be used, for individual subject plots by time, the actual PK sampling time will be used.

### ***6.3.3. Concentration of sisunatovir from paired samples obtained via microsampling compared to venous sampling.***

AUC12 and Cmax derived from blood samples collected using the Tasso® M20 device adjusted for B/P ratio will be summarized for sisunatovir and will include the set of summary statistics as specified in [Table 3](#). Summary statistics (N, geometric mean, geometric CV, median, arithmetic mean, CV, minimum, maximum) of the whole blood concentrations, plasma equivalent concentrations by microsampling using individual B/P ratio and plasma equivalent concentration by microsampling using population geometric mean B/P ratio at

nominal time of collection as defined in SoA of the protocol for each treatment arm will be calculated.

Furthermore, to determine correlation in concentrations derived from time matched Tasso® M20 microsampling (calculated using individual or population) and traditional venous plasma sampling, Bland-Altman plot analysis will be performed to evaluate the bias and SD of the bias between the mean differences and to estimate an agreement interval within a 95% confidence limit. Plots of the difference between the two samples (on Y-axis) as a function of the average of the two samples (on X-axis). These plots will be colored by participant in addition to by timepoint. In addition, a correlation plot of the plasma PK sample (on X-axis) and Tasso PK sample (on Y-axis) will be created including a line of equality  $Y = X$ . These results will be reported in a separate Clinical Bioanalytics summary report and may not be included in the CSR.

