12-Lead ECG (triplicate)	X		X						X	X	X	X	X	X	X	X		X		
 Refer to Section 8.4.4 Single ECG for Screening. Pre-dose ECGs are 3 sets of triplicates approximately 40 min, 25 min, and 10 min before pre-dose meal. All other ECGs are triplicate.
Vital Signs (BP, PR)	X		X					X		X			X			X		X		

PFIZER CONFIDENTIAL

CT02-GSOP Clinical Pharmacology Protocol Template (01 April 2022)

Page 20

Table 1. Study Schedule of Assessment

Visit Identifier Abbreviations used in this table may be found in Appendix 10.	Screen	Period 1 to Period 3														F/U Call	ET	Notes		
		Day -28 to Day -2	Day -1	Day 1	Day 2				Day 3							Day 4	31-38 Days			
Hours After Dose			0	1.5	4	5	6	12	0	1.5	3	4	5	6	8	12	24			
HIV, HBsAg, HBsAb, HBcAB, HCVAb	X																			
COVID-19 related procedures	X	X	→	→	→	→	→	→	→	→	→	→	→	→	→	→	X	X		
Study intervention administration			X	X					X											

Table 1. Study Schedule of Assessment

Visit Identifier Abbreviations used in this table may be found in Appendix 10.	Screen	Period 1 to Period 3															F/U Call	ET	Notes		
		Day -28 to Day -2	Day -1	Day 1	Day 2				Day 3								Day 4	31-38 Days			
Hours After Dose					0	1.5	4	5	6	12	0	1.5	3	4	5	6	8	12	24		
Pharmacokinetic blood sampling			X		X	X	X	X	X	X	X	X	X	X	X	X	X	X	X	X	
Pharmacokinetic microsampling (Tasso®)					X	X	X	X	X												
Blood/Plasma ratio sampling						X		X													
CRU discharge																		X			
Serious and nonserious AE monitoring	X	→	→	→	→	→	→	→	→	→	→	→	→	→	→	→	→	→	X	X	

PFIZER CONFIDENTIAL

CT02-GSOP Clinical Pharmacology Protocol Template (01 April 2022)

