The administration of sisunatovir was well tolerated at all doses, dosage forms and dosing regimens tested. In the adult healthy participants treated to date, the occurrence of TEAEs considered related to sisunatovir has been low. Most commonly reported treatment-related TEAEs were in the GI disorders SOC; nausea, diarrhea and abdominal pain. These TEAEs have been mild to moderate in intensity and resolved without sequelae. Most events attributed to IMP involved the gastrointestinal tract with nausea, diarrhea, and abdominal pain/discomfort/distension being the most common and occurring more commonly with the 350 mg dose of sisunatovir than with the 200 mg sisunatovir dose, where the number of participants reporting these events were lower or similar to those on placebo. In children, sisunatovir is required to be suspended in a solution to enable oral administration, there has been evidence of poor tolerability when sisunatovir was suspended in water as a single dose of 2.0 mg/kg in children aged 6-36 months, resulting in expulsion of the oral dose. Suspension in breast milk, formula milk or saline appeared to improve the palatability, with all doses being successfully administered to children aged 1 to 36 months in ongoing study C5241003.

As of 28 October 2022, there have been no SAEs attributable to sisunatovir and no deaths in the clinical studies.

In adults, under both fasting and fed conditions sisunatovir is slowly absorbed reaching maximum plasma concentrations (t_{max}) at 5-6 hours (hrs) with a relatively moderate

clearance, resulting in a half-life of 7-10 hours in healthy participants. Dosing to steady state resulted in steady state concentrations being reached after approximately 2 days of dosing resulting in 2-4 fold accumulation of exposure. AUC and C_{max} values increased in a greater than dose proportional manner across single and multiple dose studies. Following 5 days of dosing, the variability in PK parameters was high, with % CV ranging from 67.4-84% for C_{max} and 71.9-144% for AUC₁₂.

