4. STUDY DESIGN

4.1. Overall Design

This is a Phase 1, multiple-dose, randomized, 3-treatment, 3-period cross-over, 6-sequence, sponsor-open, placebo-and positive-controlled study to be conducted in approximately 42 adult healthy participants under fed conditions. Approximately 42 participants will be randomized into 6 sequences with 7 participants in each sequence. Participants assigned to treatment A will receive [REDACTED] oral doses of sisunatovir administered CCI [REDACTED] over [REDACTED] days in a

fed state. Participants assigned to treatment B will receive [redacted] oral doses of matching placebo administered [redacted] CCI [redacted] over [redacted] days in a fed state. Participants assigned to treatment C will receive [redacted] oral doses of placebo administered [redacted] CCI [redacted] for [redacted] days followed by a single dose of 400 mg moxifloxacin on the morning of Day [redacted]. Treatment assignments to sisunatovir and placebo will be blinded to the participants, investigator and CRU staff (except pharmacy staff) but open to the sponsor. Moxifloxacin administration on Day [redacted] will be unblinded.

For individual participants, the total duration of participation from the screening visit to the follow-up visit will be approximately 14 weeks. Screening evaluation will occur within the 28 days prior to dosing in the first treatment period. During each treatment period, eligible participants who meet the entry criteria will be admitted on Day -1, prior to treatment administration on Day 1, and will reside in the PCRU until completion of protocol assessments on Day 4. Participants may be discharged between study periods at the discretion of the investigator. There will be a washout of at least 7 days between dose administrations in consecutive crossover treatment periods. Follow-up contact will be made at least 28 calendar days and up to 35 calendar days after the last administration of the investigational product to capture any potential AEs and concomitant treatments, and to confirm appropriate contraception usage. Contact with the participant may be done via phone. For each participant, the duration of participation from Period 1 admission to discharge will be approximately 4 weeks. The follow-up call will occur up to 5 weeks after last dose of study drug.

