#### 3.3.3. Concentration of sisunatovir from paired samples obtained via microsampling compared to venous sampling.

Day 2 PK samples (traditional venous collection) and time matched PK microsamples (dried blood using the Tasso® M20 device) will be collected in Period 1 only at time points specified in the SoA of the protocol. Furthermore, at the 5 hour and 12-hour time point on Day 2, an aliquot of the PK blood sample collection will be taken and used to determine the concentration of sisunatovir in whole blood.

For each individual, blood to plasma (B/P) ratios will be calculated by dividing concurrent (i.e. Day 2, at 5 hour and 12 hour post-dose) whole blood sisunatovir concentration with the plasma sisunatovir concentration and the geometric mean B/P ratio will be calculated. A

population geometric mean of the B/P ratio from all individuals will also be calculated. Missing values will not be imputed. The plasma equivalent sisunatovir concentration by microsampling will be calculated by dividing the whole blood sisunatovir concentration with the individual geometric mean B/P ratio. As a sensitivity analysis, the plasma equivalent concentration will also be calculated using the population geometric mean B/P ratio.  $AUC_{12}$  and  $C_{max}$  will be derived from blood samples collected using the Tasso® M20 device, and then adjusted for B/P ratio.

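### The microsampling agreement limits are set on raw concentration differences with no participant term, although the plan's own plasma conversion makes part of the error proportional and shared within participant

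*SAP*

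**What the plan says.** SAP 6.3.3 compares time-matched Tasso and venous concentrations. It states that "Bland-Altman plot analysis will be performed to evaluate the bias and SD of the bias between the mean differences" and that the analysis is also "to estimate an agreement interval within a 95% confidence limit". The display is described as "Plots of the difference between the two samples (on Y-axis) as a function of the average of the two samples (on X-axis". No log, ratio or percentage difference is named, and there is no rule for spread that changes with concentration. On repeated pairs from one person, the only provision is that "These plots will be colored by participant in addition to by timepoint".

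SAP 3.3.3 says the paired Day 2 samples "will be collected in Period 1 only at time points specified in the SoA of the protocol". It converts Tasso values to plasma equivalents by dividing them by the participant's geometric mean blood-to-plasma (B/P) ratio, which is estimated at 5 and 12 hours. A single population ratio is used as a sensitivity analysis.

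SAP 6.3.3 also plans summaries with geometric means and geometric CVs and a correlation plot with a line of equality. It allows the results to be reported outside the CSR.

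**The concern.** A single pair of limits on the raw scale assumes that the spread of the differences is about the same at all concentrations. Here the concentrations cover a wide range. Protocol 2.2.4 says of five days' dosing that "the variability in PK parameters was high" (CV 67.4-84% for Cmax), and one source of error is multiplicative by construction. If most of the error behaves that way, the limits describe low concentrations too pessimistically and high ones too optimistically. Agreement at high concentrations is what bears on Cmax.

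The second issue is that several pairs come from each participant and share a conversion factor. Any standard error computed as if they were independent would be too small. At stake is how far the exploratory microsampling result can be trusted near peak concentrations.

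**Working it through.** The documents give no sample size, precision target or acceptance limit for this comparison, so there is no figure of the plan's own to reproduce.

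**Number of pairs**
- Protocol 4.1: "Approximately 42 participants will be randomized into 6 sequences with 7 participants in each sequence". If the six sequences are all orderings of three treatments, two of the six start with sisunatovir: 2 x 7 = 14 participants in Period 1.
- Protocol 6.4.4: placebo samples are not routinely assayed, so usable pairs come from about these 14.
- Protocol 1.3: the row beginning "Pharmacokinetic microsampling (Tasso" carries five marks, read as Day 2 at 1.5, 4, 5, 6 and 12 hours. Column alignment is uncertain, so six is carried as an upper case for the standard error.
- Total: 14 x 5 = 70 pairs.

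**Why part of the error is proportional and shared**

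Let P be the true plasma concentration and f the fractional error in a participant's B/P ratio. The plasma equivalent is P/(1+f).
- Raw difference: P/(1+f) - P, which is proportional to P.
- Log ratio: -ln(1+f), which does not depend on P.

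Take f = 0.10 (illustrative) and the two geometric mean Cmax values in Protocol Table 3:
- At 97.9 ng/mL: 97.9/1.10 - 97.9 = -8.9 ng/mL.
- At 811.0 ng/mL: 811.0/1.10 - 811.0 = -73.7 ng/mL.
- Log ratio at both: -ln(1.10) = -0.095.

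The same f applies to all of that participant's pairs. With the population ratio, the participant's departure from that ratio takes the place of f and is again multiplicative and shared.

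**Coverage of the limits**

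This was simulated with 2,000 trials per setting, each of 14 participants x 5 pairs. Limits were the mean ± 1.96 SD of all pooled pairs, and coverage was checked on new pairs.
- From the documents: between-participant CV 41% and 65% (Protocol Table 3) and 84% (Protocol 2.2.4).
- Assumed: time profile 0.5/0.9/1/0.95/0.55 of peak; log-normal scatter of 0.15 around it; venous CV 5%; Tasso within-participant CV 15% with participant-level CV 0, 5 or 10%, and within-participant CV 10% with participant-level CV 15%.

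| Error model and scale | All pairs | Lowest third | Top third | Top tenth |
|---|---|---|---|---|
| Constant, raw (CV 65%, independent pairs) | 94.4% | 94.5% | 94.4% | 94.4% |
| Proportional, raw | 91.8-93.2% | 99.8-100% | 77.4-82.3% | 56.9-68.4% |
| Proportional, log ratio | 92.7-94.4% | 92.8-94.5% | 92.5-94.3% | 91.7-94.0% |

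SAP 5.2 would pool two doses in the sisunatovir group if the dose is raised. That would widen the range and is not in the simulation.

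**Precision if all pairs are treated as independent**

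The true SE divided by the naive SE is √(1 + (k-1) x ICC), with k pairs per participant and an assumed within-participant correlation (ICC).
- k = 5, ICC 0.2: √1.8 = 1.34, so the naive SE is 1 - 1/1.34 = 25% too small.
- k = 5, ICC 0.5: √3.0 = 1.73, so 42% too small.
- k = 6, ICC 0.5: √3.5 = 1.87, so 47% too small.
- At k = 5 the 70 pairs are worth 70/1.8 = 39 independent pairs at ICC 0.2, and 70/3.0 = 23 at ICC 0.5.

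In the raw-scale simulation, a nominal 95% interval for the bias from pooled pairs covered 94-95% with no participant-level error, 91-92% at participant-level CV 5%, 82-84% at 10% and 68-71% at 15%. On the log scale with a participant-level SE (13 df) coverage was 94.4-95.6%.

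**The case against.** The strongest reply is that the loss of coverage comes from an error model that the documents do not contain. That stands: with constant error the raw limits reach 94.4% in every band, and under proportional error overall coverage is still 91.8-93.2%. The multiplicative conversion shows that a proportional component exists, but not that it dominates.

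A reader might also infer that the plan will report a falsely precise bias. The documents do not support this. SAP 6.3.3 names a bias, an SD and an agreement interval; its wording on the 95% level is unclear, but it does not explicitly plan an SE or confidence interval for the bias. Clustering has little effect on the bias estimate or on pooled limits, as the log-ratio row of the table shows.

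Nor does the SAP wholly ignore repeated pairs, because colouring by participant makes them visible, although it changes no estimate. This is also not the whole microsampling analysis, given the geometric summaries and the correlation plot. Log-scale treatment of Cmax and AUC24 in SAP Table 2 is for descriptive statistics and does not conflict with a raw difference plot.

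Finally, the planned plot would itself reveal fanning, and no acceptance rule depends on the limits. Both points are fair and keep the matter minor. However, the SAP does not say what would follow if fanning appeared.

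**Conclusion.** The point holds as a minor improvement. SAP 6.3.3 describes untransformed differences and does not model about five pairs from each of about 14 participants, while SAP 3.3.3 introduces error that is at least partly proportional and shared.

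If proportional error dominates, the raw limits are too wide at low concentrations and too narrow near the peak, to the extent shown above. To say outright that they fail at high concentrations would go beyond the documents. The 25-47% shortfall in the SE rests on the assumed ICC of 0.2-0.5 with five to six pairs, and it matters only if an interval is computed from pooled pairs. The consequences are confined to an exploratory endpoint that may stay out of the CSR.

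**What to change.** In SAP 6.3.3:
- Make the main agreement analysis the log of Tasso plasma equivalent over venous plasma, with a random participant effect.
- Report the geometric mean ratio with its confidence interval.
- Report 95% limits of agreement as ratios, built from the sum of the between- and within-participant variances.
- State that the 95% interval means limits of agreement.
- Keep the raw difference plot as a display.

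The cost is a few lines of SAP text and code, with no new data. The downside is that pairs with a value below the limit of quantification, which SAP 5.3 sets to zero in data presentations, drop out of the ratio; their number should be reported.
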